Initial RP2D of MS-553 for the combination is expected to be reached before the dose escalation reaches 250 mg BID, the high dose level of MS-553 under testing as monotherapy. Intermediate dose levels (i.e. at 25 mg increment) or even lower dose levels may also be evaluated as determined by the Investigators, the Safety Review Committee and Sponsor until the MTD or initial RP2D for the combination is determined.

Cohort C2. After the MTD or initial RP2D is identified for the combination of MS-553, venetoclax and rituximab, an expansion cohort of approximately 20 patients will be initiated. Treatment experienced CLL/SLL patients, eligible for standard of care venetoclax and rituximab, who are naïve to prior Bcl-2 inhibitor treatment and who have had no more than 2 prior lines of treatment regimens are eligible for this cohort to further confirm the safety of the combination and assess early evidence of anti-tumor activity. Venetoclax will be initiated on Cycle 3 following the administration of MS-553 and rituximab combination for two cycles. For this reason, the DLT evaluation period for the triplet combination is extended to 4 cycles of therapy in order to include ramping up of the venetoclax dose that is introduced in Cycle 3.

Patients in Cohort C1 and C2

Patients will be treated in 28-day cycles provided they continue to tolerate the drug, have no evidence of progression, and do not meet any of the criteria for discontinuation. All patients will continue to be monitored for approximately 30 days (+7 days) after treatment discontinuation for development of any late treatment emergent adverse events. Any adverse events noted during the DLT evaluation periods will be considered in the determination of the maximum tolerated dose/initial RP2D and dose schedule to be taken forward into the expansion phase of the study.

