2.3. Cohort C Objectives

2.3.1. Primary Objective

The primary objectives of Cohort C are to:

- Evaluate the safety of MS-553 in combination with venetoclax and rituximab in patients with CLL/SLL.
- Determine the MTD or the initial RP2D of MS-553 in combination with venetoclax and rituximab.

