3.3.4. Dose Escalation: Combination Cohort C1

Once the MTD or initial RP2D is established for the monotherapy (Cohort A1), enrollment in Cohort C1 will begin. Starting with cycle 1, patients will be dosed with MS-553 by mouth twice daily beginning at 150 mg BID, and rituximab will be started according to standard of care, and as outlined in Section 5.2.3.3. Beginning with Cycle 3, venetoclax dosing once daily by mouth will be initiated with weekly dose escalations from 20 mg to 400 mg over 5 weeks.

At least two dose levels are planned for Cohort C1. The dosing schedule and DLT evaluation periods are described in the table below.

Dose	Cycle 1	Cycle 2	Cycle 3	Cycle 4+	DLT
level					Period(s)
150 mg	150 mg	150 mg	150 mg	150 mg	Cycle 1
BID	BID	BID	BID	BID	through 4
200 mg	200 mg	200 mg	200 mg	200 mg	Cycle 1
BID	BID	BID	BID	BID	through 4

 Table 5:
 Dosing Schedule and DLT Evaluation Periods for Cohort C1

MTD determination, DLT and safety assessments will follow the general principles outlined in Cohort A1. Initial RP2D of MS-553 in the combination therapy is expected to be reached before or when the dose escalation reaches 250 mg BID, the high dose level of MS-553 under testing as monotherapy. Intermediate dose levels (i.e., at 25 mg increment) or lower dose levels may also be evaluated as determined by the Investigators, the Safety Review Committee and Sponsor until the MTD or initial RP2D for the combination is determined.

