3.5. Safety Review Committee

The SRC will monitor the safety of all patients in the dose escalation segment. The Committee will receive all available demographics, PK, and safety data (including, but not limited to, lab and ECG results, physical exam findings, vital signs, adverse events) for all patients dosed within a given cohort in order to make a decision regarding dose escalation to the next dose level. Based on the SRC's review, a dose escalation cohort may be expanded or an intermediate or a lower-than-planned dose level may be evaluated. The SRC will include the Sponsor representatives, the medical monitor, and Principal Investigators.

A separate Safety Management Plan outlines the roles and responsibilities for those involved in the collection and processing of Serious Adverse Events (SAEs), and pregnancies for this clinical study.

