APPENDIX 1C: STUDY CALENDAR C COHORTS (TRIPLET REGIMEN MS-553 + RITUXIMAB + VENETOCLAX)

Visit Evaluation Schedule

Study Cycle (28 days)	0		1		2			3			4+	ЕОТ ^а	S/RFU ^b
Cycle day ⁱ Study Procedure/Assessment	Screening ^h	1	2	84	1 (± 3 days)	1 (±3 days)	2	8	15	22	1 (±3 days)	±7 days	Q12 wks ±7d for response or Q24 wks ±7d for survival
MS-553 PO BID		Х			х	х					х		
Venetoclax PO QD (5 week ramp up dose) ^{r,p}						х	х	х	х	х	xp		
Anti-CD20 mAb (rituximab) $^{ m p}$		х			х	х					xp		
			Proce	dures				-					-
Informed Consent	х												
Confirmation of inclusion/exclusion criteria	х												
Demographics	x												
Medical History and Physical Exam	х	х	х	* ^q	х	х		х	х	х	х	Х	х
Concomitant medication survey	х	х	х	* ^q	х	х	Х	х	х	х	х	Х	
Adverse Events Assessment ^O		х	х	* ^q	х	х	Х	х	х	х	х	Х	
Vital signs; height ^k /weight	х	х	х	* ^q	х	х		х	х	х	х	Х	х
WHO/ECOG Performance Status	х	х	х	* ^q	х	х					х	Х	х
Electrocardiogram ^j	x	х		х ^q	х								
Flow Cytometry ^l	х	See note	See note	See note	See note m	See note m		See	note r	n	See note m	See note m	
		L	aborato	ry Studie	25								
Complete blood count with differential	x	x	x	* ⁴	х	x	х	х	x	х	x	х	x

[figure not shown]
Study Cycle (28 days)	0		1		2			3			4+	ЕОТ ^а	S/RFU ^b
Cycle day ⁱ Study Procedure/Assessment	Screening ^h	1	2	8 4	1 (± 3 days)	1 (±3 days)	2	8	15	22	1 (±3 days)	±7 days	Q12 wks ±7d for response or Q24 wks ±7d for survival
Serum chemistry ^e	х	х	х	× ^q	х	х	х	x ^r	xr	x ^r	х	Х	
Urinalysis	х												
Urine pregnancy test ^f	х												
HIV Ab, Hepatitis C Ab, HBsAg, anti- HBcAb	х												
Interphase FISH and stimulated cytogenetics ⁿ	х												
IGHV mutation status ^h	xx												
		Ra	adiograp	hic Stud	ies								
CT scans ^g	х					xq					x ^g		х
		Explora	tory (Co	rrelative) Studies								
Pharmacokinetic sample s			Se	e Sectio	n 6.2.3 and Tab	le 7							
Correlative Science samples	See Section 6.3.2 and Table 8						See Section 6.3.2 and Table 8						

Footnotes:

- a. EOT (End of Therapy) visit; should occur 30 ± 7 days after last dose of study drug or prior to the start of a new anticancer therapy, whichever is sooner.

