- i. Beginning in Cycle 2, a window period of +3 days is permitted for assessments and procedures to accommodate public holidays and other emergency or unforeseen situations; however, every effort should be made to have visits correspond to Day 1 of the following cycle.
- j. The ECG will be performed in triplicate at each time-point; all 3 ECG recordings should be completed within 5 minutes. Patient must rest in supine position for at least 5 minutes prior to recording an ECG. C1D1, C1D8 and C2D1 ECGs will be recorded 3 hours (± 15 minutes) following MS-553 administration in the clinic. ECGs should be recorded prior to any blood draw required at the same time-point [e.g., 3 hours (± 15 minutes) post dose ECGs on C1D1 and C1D8 should be recorded prior to 3 hours post dose blood draw]. The QTc from the electrocardiogram should be recorded on the case report form.
- k. Documentation of height is only required at screening. Weight should be collected at all visits.

I. Flow cytometry will be performed at screening on both bone marrow (when available) and peripheral blood samples (all patients). If a bone marrow aspirate/biopsy is performed to confirm a CR, flow cytometry should be performed on the bone marrow sample.

[figure not shown]
- q. CT scans can be performed prior to starting venetoclax treatment to allow for restaging, allowing outpatient therapy if TLS risk is reduced.
- r. While day 9, Day 16 and Day 23 are not on the study calendar, blood chemistry monitoring at 24 hour post venetoclax dose is recommended for the first dose of 50mg for all patients (i.e., day 9) and for the subsequent ramp-up doses for high tumor burden patients (i.e., day 16 and day 23). Please refer to venetoclax package insert.

[figure not shown]
s. For patients who have achieved complete responses with the treatment of MS-553, venetoclax, and rituximab, assessments of uMRD in a central lab will be performed in a fashion consistent with IWCLL 2018 guideline. If uMRD in both peripheral blood and bone marrow is confirmed via a central lab, MS-553 may be discontinued at the discretion of the investigators after completion of venetoclax administration as defined in its package label.

[figure not shown]

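### Cohort C schedules no ECG after venetoclax starts, so the planned ECG data describe only MS-553 plus rituximab

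*Combined protocol and SAP*

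**What the plan says.** - **ECG timing.** In Appendix 1C the ECG row is marked at screening, C1D1, C1D8 and C2D1. Footnote j matches it: "C1D1, C1D8 and C2D1 ECGs will be recorded 3 hours", counted from the MS-553 dose. Each ECG is done in triplicate. Section 6.2.1 lists ECGs among the safety assessments but leaves their timing to the calendars.
- **Venetoclax timing.** Section 3.3.4 (the ramp-up period is in weeks): "Beginning with Cycle 3, venetoclax dosing once daily by mouth will be initiated with weekly dose escalations from 20 mg to 400 mg over 5". Section 5.2.3.3 confirms that none is given earlier. Cycles 1 and 2 are MS-553 plus rituximab.
- **DLT window.** The synopsis says the window for the triplet is "extended to 4 cycles of therapy in order to include ramping up of the venetoclax dose", that is, Cycles 1 through 4 (16 weeks).
- **Purpose.** Section 2.3.1 gives a primary objective of Cohort C as "Evaluate the safety of MS-553 in combination with venetoclax and rituximab in patients with CLL/SLL". Section 3.5 gives the SRC "safety data (including, but not limited to, lab and ECG results" and other items for its dose-escalation decisions.
- **Other ECG provision.** Section 6.1.10 calls for serial ECGs only in patients on an approved QT-prolonging co-medication.

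**The concern.** Several Cohort C assessments were fitted to the delayed venetoclax start. The DLT window was lengthened. Table 7 puts C1 pharmacokinetic (PK) sampling at C3D8, C4D1 and C5D1. Section 6.3.3 puts the C1 PKC-β samples in Cycle 4. The first on-treatment CT moved from after Cycle 3 to after Cycle 2. The ECG timing did not move: footnote j is the same as in Appendices 1A and 1B apart from naming MS-553 as the dose. It still refers to a 3-hour post-dose blood draw on C1D1 and C1D8, where Table 7 shows no Cohort C sample. In Cohort B this does no harm, because acalabrutinib starts on C1D1 and the ECGs cover the combination. In Cohort C they cover only the run-in.

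The protocol treats QT as a matter to watch. It excludes a baseline QTcF above 480 msec, restricts QT-prolonging drugs and asks for timed triplicate ECGs. Section 5.2.5 also advises six hours between MS-553 and venetoclax because of a possible P-gp interaction. Under Section 3.3.5 a non-hematologic toxicity of Grade 3 or higher that does not resolve within 7 days can be a DLT. A silent QTc change could enter that count only if someone takes an ECG, and none is scheduled on the regimen being judged.

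**Working it through.** The plan gives no figure to reproduce here, so the check is calendar arithmetic. Nominal study day = (cycle − 1) × 28 + cycle day, with the 28-day cycle from Section 3.2.

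| Event | Visit | Nominal day |
|---|---|---|
| ECG | C1D1 | 0 × 28 + 1 = 1 |
| ECG | C1D8 | 0 × 28 + 8 = 8 |
| ECG (last) | C2D1 | 1 × 28 + 1 = 29 |
| Venetoclax starts | C3D1 | 2 × 28 + 1 = 57 |
| Ramp-up week 5 starts | C4D1 | 3 × 28 + 1 = 85 |
| DLT window ends | C4D28 | 3 × 28 + 28 = 112 |
| Next cycle visit | C5D1 | 4 × 28 + 1 = 113 |

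- Gap from the last ECG to the first venetoclax dose: 57 − 29 = 28 days. With the ±3 days in the column headings at both visits, it is 22 to 34 days. The order cannot reverse.
- Venetoclax days in the DLT window: 112 − 57 + 1 = 56 of 112 (50%).
- Days in the window after the last ECG: 112 − 29 = 83 of 112 (74%).
- Scheduled ECGs on the triplet: 0 in the window and 0 afterwards.
- Patients affected: 3 + 20 = 23 to 12 + 20 = 32, using the synopsis figures for C1 (3 to about 12) and C2 (about 20). Section 3.1.3 instead gives the C1 range per dose group; with two groups the upper end would be 2 × 12 + 20 = 44.

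**Is one pre-venetoclax ECG spare?** C1D8 is 7 × 24 = 168 h after the first dose. At the 10 to 14 h half-life in Section 1.2.4, that is 168/14 = 12 to 168/10 = 16.8 half-lives. The MS-553 dose is flat across cycles (Table 5). C1D8 and C2D1 are therefore both steady-state readings of the same dose. The half-life comes from healthy volunteers after single doses, so this is an assumption for patients.

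**Which later visit?** Three hours after MS-553 lies within the stated Tmax of 2 to 4 h, so the existing timing can be kept. Venetoclax is taken at least 6 h after the morning MS-553 dose (Section 5.2.3.3). An ECG 3 h after that morning dose therefore reflects venetoclax from the day before. On C4D1 that is the last day of ramp-up week 4. On C5D1 it follows 112 − 85 + 1 = 28 days from the start of week 5, but falls one day after the DLT window closes.

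**The case against.** The strongest reply is that safety on the triplet is still assessed. Adverse events and DLTs are collected through Cycles 3 and 4. Investigators can take unscheduled ECGs, and Section 6.1.10 requires serial ones for some patients. In C1, MS-553 is profiled from pre-dose to 6 h at C4D1 and C5D1, so a rise in exposure could be seen without symptoms. This stands as partial cover. It is not a substitute: clinically prompted ECGs are not systematic, and concentrations are not QTc readings. As Table 7 reads, Cohort C also has no sample in Cycles 1 and 2, so a patient's triplet profile has no earlier profile of the same patient to compare with.

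A second reply concerns Day 8. The C1D8 mark carries a *q*, but the printed footnote q is about CT scans before venetoclax. Appendix 1B limits Day 8 to Cohort B1, and a similar limit to C1 is possible, although Section 6.1.12 lists C1D8 as mandatory. If Day 8 does not apply to C2, those patients have two on-treatment ECGs, and C2D1 is their only steady-state reference. This stands and shapes the fix. The count after venetoclax is zero either way.

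A reader might infer more: that QT safety is a primary endpoint left unmeasured, or that a QTc effect would surface only through symptoms. The documents do not support this. The primary endpoint is DLTs and adverse events leading to discontinuation (Section 2.4), and ECGs outside the schedule remain possible. Nor do the documents report a QT signal for MS-553 or state the direction of any effect of venetoclax on its exposure.

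**Conclusion.** The gap is real. The calendar row and footnote j agree, no other section schedules a later ECG for all Cohort C patients, and no visit window closes the gap. None of the two or three scheduled on-treatment ECGs per patient falls on the triplet, in about 23 to 32 patients. The scheduled ECG data reaching the SRC for C1 decisions would describe MS-553 plus rituximab.

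This does not invalidate the primary endpoint or show a hazard. It means the plan would hold no systematic QTc data on the regimen whose safety is the objective, which is cheap to correct. The conclusion rests on the calendar as it can be read: some Appendix 1C footnotes are missing from the available text, but the ECG row cites only j and, on Day 8, q. The fact that q does not fit leaves uncertain who has the Day 8 ECG. It does not affect whether any ECG follows venetoclax.

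**What to change.** In Appendix 1C and footnote j, move one existing on-treatment triplicate ECG, still 3 h after MS-553, to a visit after venetoclax starts that the SRC can use when it reviews Cycles 1 to 4:

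- **C4D1 (Day 85):** inside the DLT window and already a full MS-553 PK day in C1, but at the start of ramp-up week 5.
- **C5D1 (Day 113):** a full cycle from the start of week 5, with a full PK profile in C1 and a pre-dose sample in C2. Choose it only if the protocol states that the SRC review and the DLT rules include this end-of-Cycle-4 visit.

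Keep one steady-state ECG from before venetoclax in every patient as the within-patient reference. Where C1D8 is done, keep it and move C2D1. Where it is not, keep C2D1; the only other on-treatment ECG to move is then C1D1, unless one is added.

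At the same time, correct the *q* on the Day 8 column, state whether Day 8 applies to C2, and reconcile the clinic-administered dose days in Section 5.2.3.1 (C1D1, C1D8, C2D1) with the new ECG day. Both candidate visits sit in the Cycle 4+ column, so the footnote must name the cycle.

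The cost is one row, one footnote and that reconciliation, with the number of ECGs unchanged if one is moved. There are two downsides: one fewer ECG in the MS-553 plus rituximab phase, and a 3-hour post-dose stay for C2 patients, who have no full PK profile at either visit.

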APPENDIX 2A: MS-553 RECOMMENDED DOSE MODIFICATIONS AND DOSE DELAYS

[figure not shown]
Worst toxic	ty Grade* (value)		During a cycle of therapy
Hematology	1		
<0.5 x 3	4 neutropenia without 10 ⁹ /L), unless the neu t at the time of study	tropenia was	Hold MS-553 until ANC is ≥ 0.5 x 10 ⁹ /L and until platelets recover to Grade 2 or lower per iwCLL 2018 grading.
and/or	· · · · · · · · · · · · ,	/	If treatment delay is ≤ 7 days, restart at same dose.
	018 Grade 3 or above ocytopenia:		If treatment delay is > 7 days but \leq 28 days, restart at lower dose.
Grade	Decrease in platelets† from ^ baseline value, %		If treatment delay > 28 days, discontinue study treatment
0	No change to 10	-	
1	11-24	-	
2	25-49	-	
3	50-74	-	
4	≥75		
life-thr a resul from b †Platel levels f decrea this wi unless in the i was pr patient	es: 1, mild; 2, moderate eatening; 5, fatal. Deat t of toxicity at any leve aseline will be recorded et counts must be belo for grades 1-4. If, at any se the platelet count is il be considered grade a severe or life-threate nitial platelet count (e. esent at baseline, in wh t is not evaluable for to oble to platelet counts.	h occurring as l of decrease d as grade 5. w normal r level of $<20 \times 10^{9}/L$, 4 toxicity ming decrease g., 20 $\times 10^{9}/L$) hich case the	

Grade 3 Febrile Neutropenia (ANC <1.0 x 10 ⁹ /L with fever)	If ANC at study entry was $\geq 1.0 \times 10^9$ /L:	
	• Hold MS-553 until ANC is $\geq 1.0 \times 10^9/L$	
	If ANC at study entry was < 1.0 x 10 ⁹ /L due to bone marrow involvement:	
	 Hold MS-553 until ANC returns to pretreatment level 	
	If treatment delay is ≤ 7 days, restart at same dose	
	If treatment delay is >7 days but ≤ 28 days, restart at lower dose.	
	If treatment delay >28 days, discontinue study treatment	
Nausea, Vomiting or Diarrhea with maximal prophylaxis		
Grade 3	Hold MS-553 dosing until improved to grade 1 or baseline, then restart at lower dose level for MS-553	
Grade 4	Hold MS-553 dosing until improved to grade 1 or baseline. If improves in <24 hours, restart at lower dose for MS-553	
	If grade 4 GI toxicity persists > 24 hours despite optimal use of SoC, discontinue treatment with MS-553.	
All other Toxicities		
≥ Grade 3	Hold MS-553 until improved to ≤ Grade 1 or baseline. If treatment delay is < 7 days, restart at same dose or at a lower dose level upon agreement between the investigator and Sponsor. If treatment delay is >7 days but ≤ 28 days, restart at lower dose level. If treatment delay >28 days, discontinue study treatment.	

APPENDIX 2B: DOSE MODIFICATIONS OF ACALABRUTINIB

Recommended dose modifications for acalabrutinib for Grade 3 or greater adverse reactions are outlined below. Please refer to the acalabrutinib prescribing information for more specific details.

Event	Adverse Reaction Occurrence	Dose Modification (Starting dose = 100 mg approximately every 12 hours
Grade 3 or greater non- hematologic toxicities, Grade 3 thrombocytopenia with bleeding,	First and Second	Interrupt acalabrutinib dosing. Once toxicity has reserved to Grade 1 or baseline, acalabrutinib may be resumed at 100 mg approximately every 12 hours.
Grade 4 thrombocytopenia or Grade 4 neutropenia lasting longer than 7 days	Third	Interrupt acalabrutinib dosing. Once toxicity has reserved to Grade 1 or baseline, acalabrutinib may be resumed at a reduced frequency of 100 mg once daily.
	Fourth	Discontinue acalabrutinib

Г

APPENDIX 2C: DOSE MODIFICATIONS OF VENETOCLAX AND RITUXIMAB

Dose modifications or hold of rituximab can be made by the treating physicians per institutional standard.

The recommended dosage modifications for venetoclax for adverse reactions are provided in the table below. For patients who have had a dosage interruption greater than 1 week during the first 5 weeks of ramp-up phase or greater than 2 weeks after completing the ramp-up phase, reassess for risk of TLS to determine if re-initiation with a reduced dose is necessary (e.g., all or some levels of the dose ramp-up schedule).

Adverse Reaction	Occurrence	Dosage Modification	
Tumor Lysis Syndrome			
Blood chemistry changes or symptoms suggestive of TLS	Any	Withhold the next day's dose. If resolved within 24 to 48 hours of last dose, resume at same dose.	
		For any blood chemistry changes requiring more than 48 hours to resolve, resume at reduced dose	
		For any events of clinical TLS ^b , resume at reduced dose following resolution	
I	Non-Hematologic Adverse Reaction	ns	
Grade 3 or 4 nonhematologic toxicities	1st occurrence	Interrupt venetoclax. Upon resolution to Grade 1 or baseline level, resume venetoclax at the same dose.	
	2nd and subsequent occurrences	Interrupt venetoclax. Follow dose reduction guidelines when resuming treatment with venetoclax after resolution. A larger dose reduction may occur at the discretion of the physician.	

Recommended Venetoclax Dosage Modifications for Adverse Reactions^a in CLL/SLL

Hematologic Adverse Reactions			
Grade 3 neutropenia with infection or fever; or Grade 4 hematologic toxicities (except lymphopenia)	1st occurrence	Interrupt venetoclax. Upon resolution to Grade 1 or baseline level, resume venetoclax at the same dose.	
	2nd and subsequent occurrences	Interrupt venetoclax. Follow dose reduction guidelines when resuming treatment with venetoclax after resolution. A larger dose reduction may occur at the discretion of the physician.	

Consider discontinuing venetoclax for patients who require dose reductions to less than 100 mg for more than 2 weeks.

^aAdverse reactions were graded using NCI CTCAE version 5.0.

^bClinical TLS was defined as laboratory TLS with clinical consequences such as acute renal failure, cardiac arrhythmias, or sudden death and/or seizures.

The recommended dose reductions for venetoclax for adverse reactions are provided in the table below.

[figure not shown]
Recommended Dose Reduction for Adverse Reactions for venetoclax in CLL/SLL

Dose at Interruption, mg	Restart Dose, mg ^a	
400	300	
300	200	
200	100	
100	50	
50	20	
20	10	
³ During the ramp-up phase, continue the reduced dose for 1 week before increasing the dose		

[figure not shown]
^aDuring the ramp-up phase, continue the reduced dose for 1 week before increasing the dose.

Protocol MS-553-103	(v.8.1)
---------------------	---------

MingSight Pharmaceuticals, Inc.

APPENDIX 3: LIST OF CO-MEDICATIONS TO AVOID

A. Strong and moderate CYP3A inhibitors, inducers and sensitive and moderately sensitive substrates

	CYP3A4 Inducers	
apalutamide	macrolide antibiotics	primidone
bosentan	mitotane	rifabutin
carbamazepine	phenobarbital	rifampin
dexamethasone	phenylbutazone	rifapentine
efavirenz	phenytoin	sulfinpyrazone
enzalutamide	prednisone	St. John's wort
glucocorticoids		
	CYP3A4 Inhibitors	
amprenavir	elvitegravir	paritaprevir
anastrozole	erythromycin	paroxetine
aprepitant	fluconazole	posaconazole
boceprevir	fluvoxamine	propranolol
canazol	grapefruit juice	quinidine
celavirdine	idelalisib	quinine
cimetidine	imatinib	ranitidine
ciprofloxacin	indinavir	ritonavir
crizotinib	itraconazole	saquinavir
clarithromycin	ketoconazole	sertraline
clotrimazole	lopinavir	telithromycin
cobicistat	mibefradil	tofisopam
cyclosporine	miconazole	troglitazone
dasabuvir	nefazodone	troleandomycin
danoprevir	nelfinavir	verapamil
diethyldithiocarbamate	nevirapine	voriconazole
diltiazem	norfloxacin	zafirlukast
dronedarone	ombitasvir	
	CYP3A5 Inducers	
phenobarbital	primidone	troleandomycin
phenytoin	rifampin	
	CYP3A5 Inhibitors	· · · · ·
clotrimazole	metronidazole	troleandomycin
ketoconazole	miconazole	
	CYP3A Sensitive Substrates	
alfentanil	everolimus	saquinavir
avanafil	felodipine	sildenafil
buspirone	ibrutinib	simvastatin
budesonide	indinavir	sirolimus

conivaptan	lomitapide	tacrolimus	
darifenacin	lovastatin	ticagrelor	
darunavir	lurasidone	tipranavir	
dasatinib	maraviroc	tolvaptan	
dronedarone	midazolam	triazolam	
ebastine	naloxegol	vardenafil	
eletriptan	nisoldipine		
eplerenone	quetiapine		
CYP3A Moderate Sensitive Substrates			
alprazolam	colchicine	rilpivirine	
aprepitant	eliglustat	tadalafil	
atorvastatin	pimozide		

Source for CP3A information:

Tatro DS, Drug Interaction Facts: The Authority on Drug Interactions. Wolters Kluwer Health, 2012.

FDA Drug Development and Drug Interactions: Table of Substrates, Inhibitors and Inducers.

Web link Accessed 20 December 2019:

https://www.fda.gov/drugs/drug-interactions-labeling/drug-development-and-drug-interactions-table-substrates-inhibitors-and-inducers

B. Drugs that prolong QTc interval

Source for QTc drug list:

Woosley, RL and Romero, KA, www.Crediblemeds.org, QTdrugs List, Accession Date, AZCERT, Inc. [name]

Web link Accessed 23 August 2019: https://www.crediblemeds.org/

